6. SUBJECT SELECTION

6.1 Study Population

All adult patients (>18 years old) with ICD code I50* (given ICDI50.2 may not always be selected) and echo with LVEF $\leq 40\%$ within the last 24 months (24 months was chosen rather than 12 months given limited echo availability, particularly during COVID-19). Only patients with active prescription through IHS and engaged in care at our centers (clinical visit within last 12 months) will be included. Patients will be randomized to 1 of 5 clusters (which determines time of implementation). For ethical considerations, we aim to enroll all patients who meet eligibility criteria at GIMC and THC. Subjects who will be enrolled are those with a diagnosis of

HFrEF (LVEF \leq 40%) who are seen in an outpatient internal medicine or family medicine IHS clinics at GIMC or THC.

6.2 Inclusion/Exclusion Criteria

Inclusion

- Age \geq 18 years
- Seen at internal medicine or family medicine clinic at GIMC or THC in last 12 months
- Left ventricular ejection fraction \leq 40%
- Prescription at IHS pharmacy in last 12 months

Exclusion

- Primary providers opted out of inclusion for that particular patient
- Hospice care

Eligibility: Eligibility of patients will be assessed by the study team based on the patient's medical record. However, as detailed, if provider feels patient is inappropriate for enrollment, they can also opt out of enrollment. Those who meet criteria will have a EHR message sent through the chart to the primary provider. Primary providers have 1 week to opt out. If they do not opt out, patient will be automatically enrolled and placed into a randomization cluster group.

Exclusion criteria have been kept to a minimum to ensure that the study can examine the effectiveness of using this heart failure care model within a 'real world' setting.

6.3 Subject Recruitment

Eligible patients are identified as above. All primary providers will be sent a message through the EHR in the patient chart reporting that their patient is planned to be enrolled in the study. Providers can sign to consent to patient enrollment, or otherwise, can opt out of the study if their feel patient enrollment not appropriate. If a primary provider does not opt out within 7 days, then patient will be enrolled.

[figure not shown]
Eligible patients are identified through a query through iCARE, a EHR based data system through the IHS EHR. Patients with ICD10 diagnostic criteria for HF will be identified, and then all those patients will have their chart reviewed to confirm LVEF less than or equal to 40% on echo within last 24 months. The inclusion criteria will be all adults \geq 18 years, who have a prescription in the IHS system in the last 12 months, and have had a clinical visit at GIMC or THC in the last 12 months. As this is an intervention assessing a model to improve uptake of standard of care, we cannot inform patients of their participation in the study at the time of enrollment, as this would contaminate the randomized exposure. As this study presents minimal risk to patients, we requested a waiver of informed consent at the patient level.

7. INTERVENTIONS

7.2 Intervention: Heart Failure Telemonitoring Care Delivery Model

This project was implemented as an Indian Health Service Innovations Award to improve quality of care for patients. Once patients are at their intervention time point, they receive implementation of our designed HF QI model. As part of this model, all patients are given a home BP cuff (Omron 5 arm cuff) for home BP monitoring. Protocols for each step of this model are detailed in the supplement. However, in brief, as part of the intervention, these protocols allow the study team to identify which, if any recommended guideline-directed medications are missing, identify any contraindications to therapy, and initiate therapy as directed if no contraindications are identified. Prescriptions for the therapy are made, appropriate follow-up lab testing ordered if needed, and patients are called by the study team to discuss the therapy and recommendations. Getting patients are low doses of all 4 therapy (or all therapies they are eligible on) is prioritized by the study protocol, and then doses could be secondarily uptitrated per recent HF Expert Consensus Statement.[8] There are protocols for overall model, and initiation and titration of all medications. Utilizing home blood pressure monitoring, medications were added and titrated as directed by study protocols, with patients coming in for lab work as recommended by the study protocol. All medication changes, lab work, home BP and HR readings, will be documented in the EHR and sent to the PCP. Please see supplement for flowcharts utilized in this study. Overall model is shown in Figure 2.

Figure 2. Overview of Model to Improve Heart Failure Care in Navajo Nation

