	especially those living remotely and receiving care through the IHS, where cardiology care is often unavailable. The proposed pragmatic clinical trial aims to improve the quality of care of AI/AN patients with heart failure with reduced ejection fraction receiving care through the IHS. We will perform a pragmatic trial clinical that will use a stepped wedge randomized design to implement and evaluate the effectiveness of a strategy that leverages the electronic medical record to find HFrEF patients not on appropriate therapy, and initiates/optimizes GDMT through telemonitoring in the Navajo Nation.
STUDY DESIGN	This is cluster stepped wedge randomized control trial, with randomization at the patient level
PRIMARY OBJECTIVE	To evaluate if there is an increase in rates of guideline-directed medical therapy with implementation of the heart failure telemonitoring model
SECONDARY OBJECTIVES	To evaluate if there is an increase in the dose of the guideline-directed medical therapy with implementation of the heart failure telemonitoring model
NUMBER OF SUBJECTS	80-100 HFrEF patients
SUBJECT SELECTION CRITERIA	
Inclusion Criteria: This care delivery model will be applied to adult patients (age >18 years) with heart failure with reduced ejection fraction seen cared for in the Gallup Service Unit in Navajo Nation (Gallup Indian Medical Center and Tohatchi Helath Center) with at least 1 clinical encounter in past 12 months (including telemedicine), and has 1 active prescription at an IHS pharmacy in the last 12 months
 
Exclusion Criteria: Anyone not willing to participate, anyone that their primary care physician opts out as feels is inappropriate to participate, anyone on hospice care.

EFFICACY EVALUATIONS	
PRIMARY ENDPOINT	The proportion of patients who have an increase in the number of prescribed evidence-based therapies for HFrEF (beta-blockers, ACE-I/ARB/ARNI, MRA, SGLT2i) at 30 days post implementation. This endpoint is based on filling of the prescription.
SECONDARY ENDPOINTS	Secondary outcomes will include: percentage of patients prescribed each medication class (i.e. percentage on beta-blockers, percentage on ACE-I/ARB, percentage of ARNIs, percentage on SGLT2i, and percentage on MRAs), medication doses (all at 30-days as well as post-implementation at 6 months); HF hospitalizations at each time point, 6-month mortality, referrals, cardiac procedures, adverse events (to include hypokalemia [K<3.0

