3.2 Secondary Objectives

The primary objective is to assess the clinical efficacy of a heart failure care deliver model as measured by the change in rates of each GDMT therapy, the doses of each therapy, differences in HF hospitalizations, referrals, cardiac interventions, and adverse events over the study period.

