5. CRITERIA FOR EVALUATION

5.1 Primary Efficacy Endpoint

The primary outcome for the trial will be the proportion of patients who have an increase in the number of prescribed evidence-based therapies for HFrEF (beta-blockers, ACE-I/ARB/ARNI, MRA, SGLT2i) 30 days post implementation. This endpoint is based on filling of the prescription. In IHS pharmacies, we are able to differentiate between active prescriptions that are filled/picked up, and those that are “not picked up”. We will only include filled prescriptions in the primary and secondary endpoints. In addition to addition of classes of GDMT, we will also consider a change from an ACEI/ARB to an ARNI consistent with increase in the ‘number’ of GDMT given their demonstrated superior benefit.[5]

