5.2 Secondary Efficacy Endpoints

Secondary endpoints will include percentage of patients prescribed each medication class (i.e. percentage on beta-blockers, percentage on ACE-I/ARB, percentage of ARNIs, percentage on SGLT2i, and percentage on MRAs), medication doses of each therapy, all at 30-days as well as post-implementation at 6 months; HF hospitalizations at each time point, 6-month mortality, referrals, cardiac procedures. Outcomes determined by review of medical, hospital, and billing records.

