9 STUDY PROCEDURES AND GUIDELINES

9.1 Clinical Assessments

9.1.1. Baseline Medications

All baseline medications and their doses will be documented at enrollment of a patient's physician, as well as at each assessment cross-over time point. Dose, route, unit frequency of administration, will be captured. We only consider a patient to be on a medication if they have an filled prescription for the medication.

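### Of the two times named for the dose endpoint, only 30 days has concurrent randomised controls, and the controlled dose readings at 60 to 120 days that will be captured are assigned to no dose analysis

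*Combined protocol and SAP*

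**What the plan says.** The synopsis gives the secondary objective as "To evaluate if there is an increase in the dose of the guideline-directed medical therapy with implementation of the heart failure telemonitoring model". Section 3.2 is broader and lists "the doses of each therapy, differences in HF hospitalizations, referrals, cardiac interventions, and adverse events over the study period".

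The endpoint itself is narrower in time. Section 5.2 has "medication doses of each therapy, all at 30-days as well as post-implementation at 6 months", and the synopsis and section 1 name the same two times. Section 5.1 adds "We will only include filled prescriptions in the primary and secondary endpoints".

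On the order of treatment, section 7.2 says "Getting patients are low doses of all 4 therapy (or all therapies they are eligible on) is prioritized by the study protocol" and puts up-titration after that. It gives no timing; the initiation and titration flowcharts are in a supplement that is not part of the document.

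On data capture, section 9.1.1 records medications and doses at enrolment "as well as at each assessment cross-over time point". Section 4.1 likewise plans evaluations at each cross-over and at 6 months.

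On analysis, the mixed model in section 11.3 is logistic and is introduced for rates of GDMT. Continuous secondary outcomes get a generalized linear model with no assessment times, time effect or exposure term stated. Section 11 promises a detailed SAP before the final analysis.

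**The concern.** A stepped-wedge trial separates the intervention from calendar time by comparing treated clusters with clusters still in usual care on the same date. Sections 4.4 and 11.3 rely on this, because they expect care to improve over time and providers to learn from treated patients. A reading taken after the last cluster has crossed over has no such comparison.

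One of the two named dose times is in that position. The other is the earliest reading after implementation, in a model of care that places low-dose starts ahead of titration. If the dose analysis kept to the named times, the randomised evidence on dose would come only from the first month. A flat 30-day result could then be reported as showing that the model does not raise doses, while a favourable 6-month result could not be separated from the secular trend. The trial will hold controlled readings from later exposure, but the plan does not say that they will be used for dose.

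**Working it through.** **The plan's own figure.** Section 11.4 states more than 95% power for a rise from 25% to 50% on one therapy, with four clusters of 20, five time points and a 5% type I error rate. A stepped-wedge calculation on cluster-period means (fixed time effects, random cluster intercept, normal approximation, two-sided 5%), with an assumed intracluster correlation (ICC) of 0 and independent repeated readings, gives 95.5% to 96.6%. The figure is reproduced, but it concerns a proportion. The plan states no power, standard deviation (SD) or target difference for dose.

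**Inputs for the dose question.**
- Starts: days 0, 30, 60, 90 and 120 for clusters 1 to 5 (section 4.4).
- Size: 80 to 100 patients (synopsis) over five clusters, so 80/5 = 16 to 100/5 = 20 per cluster.
- Dose capture: every cross-over (section 9.1.1).
- Convention: a cluster crossing on a given day is read just before it crosses and counts as control.

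**Controlled readings by date** (exposure = calendar day minus start day).

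| Day | Treated clusters (days of exposure) | Controls | Treated beyond 30 days vs controls, patients |
|---|---|---|---|
| 30 | 1 (30) | 2, 3, 4, 5 | none vs 64–80 |
| 60 | 1 (60), 2 (30) | 3, 4, 5 | 16–20 vs 48–60 |
| 90 | 1 (90), 2 (60), 3 (30) | 4, 5 | 32–40 vs 32–40 |
| 120 | 1 (120), 2 (90), 3 (60), 4 (30) | 5 | 48–60 vs 16–20 |
| 150, 180 | all | none | no controlled comparison |

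The treated cluster-readings with controls number 1 + 2 + 3 + 4 = 10. Four are at 30 days and 1 + 2 + 3 = 6 are at 60 to 120 days. Six readings of 16 to 20 patients make 96 to 120 patient-readings. They come from clusters 1 to 3 only, so from 3 × 16 = 48 to 3 × 20 = 60 distinct patients. Under control, cluster 1 reaches 120 days, cluster 2 reaches 90 and cluster 3 reaches 60.

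The 6-month reading has no controls on either interpretation. By calendar it is day 180; counted from each cluster's own start, the earliest is also day 180 (cluster 1).

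**What those readings can detect.** For a single date, the difference detectable with 80% power at two-sided 5% is (1.96 + 0.84) × √(1/n_treated + 1/n_control), in SD units:
- Day 60 or day 120, 20 per cluster: 2.80 × √(1/20 + 1/60) = 0.72. With 16 per cluster: 0.81.
- Day 90, 20 per cluster: 2.80 × √(1/40 + 1/40) = 0.63. With 16 per cluster: 0.70.

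A single model over days 0 to 150, with six date effects and separate effects for up to 30 days and beyond 30 days, has 8 parameters. Its design matrix over 30 cluster-dates has rank 8, so both effects are estimable. The standard error of the later effect is 0.084 to 0.168 SD over ICC 0 to 0.01, within-patient correlation 0 to 0.8 and 16 to 20 per cluster. The detectable later effect is 2.80 times that, about 0.24 to 0.47 SD. The model assumes that the effect is constant within each of the two exposure bands.

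**Why the metric must be stated.** Take section 11.4's change from 25% to 50% on a drug. Suppose, as an illustration, that existing users stay at dose d and new users start at c·d, with c below 1. The mean among users moves from d to (0.25d + 0.25cd)/0.50 = d(1 + c)/2, a fall. The mean over all patients, counting those not on the drug as zero, moves from 0.25d to 0.25d(1 + c), a rise. The same data give opposite signs, and the plan does not say which mean is meant.

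**The case against.** The strongest defence is that the plan does not discard the later readings. Doses are captured at every cross-over, section 3.2 sets the dose objective over the whole study, section 11.3 does not confine continuous outcomes to 30 days, and the detail is deferred to a SAP. This stands against one inference a reader might draw, that 30 days is the only dose reading planned with concurrent controls. The documents do not support that: controlled readings up to 120 days will exist. What remains is that 30 days is the only *named* dose endpoint time with controls, and that no text says how the other readings will be analysed. The logistic model for GDMT rates does not fill the gap, since dose is not binary. A single treatment indicator would also average early and later exposure.

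A reader might also infer that titration cannot have happened by day 30. Section 7.2 gives a sequence and no timetable, and patients already on a class could be titrated sooner. That the filled dose at day 30 is usually the first fill would need a supply length of about a month, which the documents do not state.

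Nor is a null or negative 30-day result shown to be likely. If patients not on a drug count as zero, starting it raises dose by day 30.

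Finally, precision at any single later date is modest, and section 11.3 itself expects contamination of controls. Both points stand. They favour pooling all readings in one model over singling out one date or exposure window.

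**Conclusion.** The concern holds as a gap between the objective, the data captured and the stated analysis. Of the two named dose times, one has no concurrent controls and the other is the earliest after implementation. Six of the ten controlled treated cluster-readings lie beyond 30 days (96 to 120 readings, 48 to 60 patients) and have no assigned role in the dose analysis.

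The counts rest on starts exactly 30 days apart, equal clusters of 16 to 20, and crossing clusters being read before they cross. If they were not counted as controls, day 120 would have none and the six would fall to three (day 60: cluster 1; day 90: clusters 1 and 2). The detectable differences are in assumed SD units.

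That 30 days largely reflects the starting phase is a reasonable inference from section 7.2 but is not established. The point concerns a secondary endpoint and does not touch the primary analysis. It is worth making because the correction is cheap and gives a randomised answer on dose beyond 30 days that the named times cannot.

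**What to change.** In sections 5.2 and 11.3, or in the promised SAP:

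1. Add every cross-over to the dose endpoint times, keeping 30 days and 6 months.
2. Analyse dose from all cross-over readings in one stepped-wedge model with fixed calendar-time effects, allowance for repeated readings within patient, and separate effects for up to 30 days and beyond 30 days since implementation.
3. State the dose metric, including how patients not on a class are counted.
4. Label the 6-month dose reading descriptive.

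No new data are needed and no change to the titration protocol is implied. The cost is a wording change (an edit to the protocol text needs prior written IRB approval under section 13.1), slightly more analysis, and less precise estimates at 90 to 120 days of exposure, where few controls remain.

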7.3 Control Condition- treatment as usual

Participants in the Control Condition will continue to receive medical treatment as usual as directed by their primary care physician. All physicians at THC and GIMC will receive a lecture at the start of the study on updated ACC/AHA/HFSA guidelines on optimal therapy for GDMT.

8. STUDY TREATMENTS

8.1 Method of Assigning Subjects to Intervention Group

Patients will be randomized assigned to 5 clusters cluster and timing group using a SAS-based computer-generated randomization scheme developed by the study PI. The investigator or designee will complete a randomization worksheet, as detailed in the Study Protocol.

8.2 Blinding of Intervention

Patients will be informed that they are enrolled in a new quality improvement program to get them on optimal therapy and thus will not be blinded to their randomization status or participation in this trial. Provider subjects will, obviously, not be blinded to the intervention as they are receiving the alert and will be consenting to participate in the study. We will engage in both pre-trial and periodic teaching and discussion with all participating care providers to inform clinicians about the nature of the study and to discuss specific factors that are being measured. The study team is not blinded to the cluster assignment as they are implementing the model. However, the outcomes will be pulled from the EHR from study members that are blinded to randomization/cluster status of the patient.

9 STUDY PROCEDURES AND GUIDELINES

9.1 Clinical Assessments

9.1.1. Baseline Medications

All baseline medications and their doses will be documented at enrollment of a patient's physician, as well as at each assessment cross-over time point. Dose, route, unit frequency of administration, will be captured. We only consider a patient to be on a medication if they have an filled prescription for the medication.

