4. STUDY DESIGN

4.1 Study Overview

This is a single ‘center’ (Gallup Service Unit- which includes two ambulatory clinics), stepped wedge cluster randomized design with 5 clusters planned. We will randomize each patient to 1 of 5 clusters, each of which has a different enrollment time point, separated 1 month apart. Each patient will receive intervention with the heart failure care delivery model at time of enrollment. Evaluations will be taken at each cross-over time point and at conclusion of 6 months. Screening data will be reviewed to determine subject eligibility. Subjects who meet all inclusion criteria and none of the exclusion criteria will be entered into the study. Prior to enrollment for each patient, a message will be sent in that patient’s chart through the EHR to the patient’s primary provider who has 7 days to opt out if they think patient should not be enrolled.

Probable Duration of Project: Total duration of subject participation will be 6 months.

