4.4. Randomization

Randomization in this study will occur at the level of the patient. This is a stepped wedge trial design, and patients will be randomized to 1 of 5 clusters. Every cluster will have the model implemented, but the time point of implementation will vary based on cluster, in 30 day increments. Cluster 1 will have the model implemented at time 0, cluster 2 at 30 days, cluster 3 at 60 days, etc (as shown in Figure 1). Prior to implementation, patients in pre-implementation time points will receive usual care. In addition, all providers received a lecture regarding updated ACC/AHA/HFSA guidelines and expert consensus prior to implementation of the model. Given the stepped-wedge design, all patients will eventually benefit from implementation of the model, but it also allows us to evaluate the effect of secular trends towards better care over time (and ensure the model rather than trends in care are not responsible for improving care).

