11.3. Analysis of Primary and Secondary Endpoints

To assess the effectiveness of our intervention, measurement of rates of GDMT, including each specific medication of ACE inhibitors, ARB, ARNI, beta-blockers, MRA, SGLT2 inhibitors will be performed at baseline, at each cross-over time point. The main analysis of our stepped wedge design will be based on a logistic mixed-effects model which will contain a random intercept to account for between-cluster variability, a fixed effect parameter for time, and a group indicator variable for the treatment for each subject and time to capture treatment differences over time.

Safety and tolerability data will be summarized by intervention group.

Adverse event rates will be coded by body system and MedDra classification term. Adverse events will be tabulated by treatment group and will include the number of patients for whom the event occurred, the rate of occurrence, and the severity and relationship to newly started therapy.

Statistical Analysis: The primary analysis will utilize the intention to treat principle. A generalized linear model will be used to assess the relationship between randomization cluster status and the primary outcome. The model will use a log-link and independent correlation structure to allow for calculation of adjusted risk ratios. Statistical significance will be based on a P value of <0.05. For categorical secondary outcomes, a similar generalized linear modeling approach will be used. For continuous secondary outcomes, a generalized linear model will be used.

Assessment of contamination: Providers may learn to better treat heart failure as consistent with evidence-based therapies over time. Given we are not clustering by provider, but rather patients, it is possible that providers will take what is being implemented on their patient that is in an active implementation phase, and apply it to a patient in a non-active implementation phase. Therefore, there is a high risk of contamination. However, with the stepped wedge design, we will be able to also see how GDMT rates increase over the study period for those clusters who are not immediately in an active implementation arm. We will be able to better understand if increases in GDMT are related to the intervention or just due to increases over time due to improved knowledge of providers over time.

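### The primary endpoint's increase has no defined starting record, and the one baseline-medication rule is tied to the physician's enrollment rather than to the patient's own cross-over

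*Combined protocol and SAP*

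**What the plan says.** Section 5.1 defines the primary outcome as "the proportion of patients who have an increase in the number of prescribed evidence-based therapies for HFrEF", read 30 days after implementation and based on filled prescriptions. It gives the end of the comparison and not its start.

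Baseline medication is dealt with in 9.1.1: "All baseline medications and their doses will be documented at enrollment of a patient's physician, as well as at each assessment cross-over time point". The sentence therefore provides for a physician-level record and, in addition, a record at each cross-over. Section 11.3 and the synopsis likewise list a baseline measurement and, separately, one at each cross-over. Section 11.4 assumes a single baseline measurement, and 3.1 speaks of the increase across the study period.

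The step timing is in 4.4: "Cluster 1 will have the model implemented at time 0, cluster 2 at 30 days, cluster 3 at 60 days, etc". Patients are the unit of randomisation (4.1, 4.4), although 4.3 in one place has physicians being randomised and 11.1 defines the analysis set through a randomised provider.

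Enrollment is used in two ways. Section 4.1 says "We will randomize each patient to 1 of 5 clusters, each of which has a different enrollment time point, separated 1 month apart" and "Each patient will receive intervention with the heart failure care delivery model at time of enrollment", which makes enrollment the patient's own start. Section 6.2 has the patient enrolled automatically if the provider does not opt out, and then placed in a cluster. No physician enrollment date is defined anywhere.

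Section 11.3 gives two models for the primary comparison: a logistic mixed model with a fixed effect for time, and a log-link generalized linear model on cluster status for which no time term is stated.

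**The concern.** An increase needs two records, and the plan names one. The only text labelled baseline points to an event that belongs to the physician. Because allocation is by patient and not by provider, two patients of one physician can start the model months apart, so a date attached to the physician cannot be the start for both. If that date lies at or near the beginning of the study, therapies that the primary provider adds while the patient waits would be included in the proportion reported 30 days after implementation.

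The plan itself expects such additions. All physicians receive a guideline lecture at the start (4.4, 7.3), and of spill-over between patients 11.3 says "Therefore, there is a high risk of contamination".

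What is at stake is the meaning of the headline proportion and, depending on how control periods are scored and whether time is modelled, the treatment comparison as well. Section 11 leaves the detailed SAP to be written before the final analysis, so as things stand the reference record could be chosen after data have accrued.

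**Working it through.** **No figure to reproduce.** The plan gives no figure for this point. The power statement in 11.4 (above 95% for 25% against 50%) concerns the proportion on one therapy, not an increase from a baseline, so the choice of reference record does not enter it.

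**Inputs.** Five clusters (4.1) starting at days 0, 30, 60, 90 and 120 (4.4), taken as equal in size; 11.4 assumes 20 patients per cluster. The usual-care rate r of adding at least one therapy per 30 days is not in the documents. I assume 1, 5 and 10%, constant over time, with no intervention effect.

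**Step 1: waiting time.** Cluster c waits 30 × (c − 1) days: 0, 30, 60, 90, 120. The mean is 300/5 = 60 days. From day 0 to the 30-day reading is 30 days in cluster 1 and 60 to 150 days in clusters 2 to 5.

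**Step 2: proportion with an increase at 30 days after implementation.**
- Counted from the patient's own cross-over record: r in every cluster.
- Counted from a day-0 record: 1 − (1 − r)^c in cluster c. At r = 5% this is 5.0, 9.75, 14.26, 18.55 and 22.62% for clusters 1 to 5, mean 14.0%.

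**Step 3: comparison with control periods scored from the same day-0 record.**
- Within calendar time: at the end of period t, cluster t (30 days into the model) and the clusters still waiting all have probability 1 − (1 − r)^t. The difference is 0 at every r.
- Ignoring calendar time: the five 30-day readings are set against the ten control-period readings (four at the end of period 1, three at period 2, two at period 3, one at period 4). At r = 5% the control mean is (4 × 5.0 + 3 × 9.75 + 2 × 14.26 + 18.55)/10 = 9.63%, and 14.04 − 9.63 = 4.4 points.

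| Assumed r per 30 days | Own cross-over reference | Day-0 reference, mean of 5 clusters | Excess (points) | Control mean, day-0 reference | Difference ignoring time (points) | Difference within calendar time |
|---|---|---|---|---|---|---|
| 1% | 1% | 3.0% | 2.0 | 2.0% | 1.0 | 0 |
| 5% | 5% | 14.0% | 9.0 | 9.6% | 4.4 | 0 |
| 10% | 10% | 26.3% | 16.3 | 18.6% | 7.7 | 0 |

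The log-link model reports risk ratios. With time ignored, the null ratios are 2.96/1.99 = 1.49, 14.04/9.63 = 1.46 and 26.29/18.56 = 1.42.

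**Step 4: a real effect under matched scoring.** If the model raises the 30-day probability from r to p, the same-period difference from a day-0 record after k waiting intervals is (1 − r)^k × (p − r), because a patient who has already increased cannot do so again. For cluster 4 (k = 3) the factor is 0.95³ = 0.86 at r = 5% and 0.90³ = 0.73 at r = 10%. Time adjustment removes the null bias but not this shrinkage.

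**The case against.** The strongest reply is that the plan does not fix baseline early. The sentence in 9.1.1 goes on to require a record at each cross-over, 11.3 repeats this, and an outcome described as 30 days after implementation is most naturally read as change across implementation. Section 4.1 can be taken to mean that enrollment is the patient's own start, and the provider message in 4.1 and the opt-out in 6.2 are handled patient by patient. On that reading there is no bias. All of this stands, except that 6.2 puts enrollment before cluster allocation, so the documents do not settle which reading applies.

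The second reply is that the mixed model has a time effect, and that matched scoring gives a null difference of 0. That also stands, but it depends on control periods being scored from the same record, which no section states. The log-link model speaks of adjusted risk ratios without naming time among the adjustments.

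Three stronger readings are tempting and not supported:
- A reader might infer that usual-care drugs are counted as intervention success by rule. No section says so; the reference is left open.
- A reader might take 14% against 5% as the bias in the comparison. That requires treated patients scored from day 0, controls scored in separate 30-day windows, and no time adjustment, a combination the plan does not describe.
- A reader might assume that each physician's patients fall in all five clusters, or that the window is mostly usual care in every late cluster. The number of providers is not given, and in cluster 2 the split would be 30 of 60 days.

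**Conclusion.** The point holds as a defect in the definition of the primary endpoint. The only baseline-medication rule is anchored to the wrong unit, and 5.1 specifies neither the starting record nor the scoring of control periods. The consequence is conditional. If the literal anchor were used and lay at study start, the reported 30-day proportion would be inflated by 2.0, 9.0 and 16.3 points at assumed usual-care rates of 1, 5 and 10% per 30 days. The comparison between conditions would carry no null bias with matched scoring and calendar-time adjustment, and about 1 to 8 points in favour of the model if time is ignored, as the log-link model's text allows.

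These sizes rest on assumed, constant addition rates, equal clusters and an anchor at day 0. The documents give no usual-care rate and no physician enrollment date, so they do not show that any of this bias would occur. They show that nothing in the text rules it out.

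**What to change.** - In 9.1.1, replace the physician-enrollment anchor with the patient's own scheduled implementation (cross-over) date.
- In 5.1, define the increase as the filled-therapy count 30 days after that date minus the count on that date, keeping the existing rule that a change to an ARNI counts as an increase.
- Score each 30-day control interval in the same way, from the cross-over record at its start. At a constant usual-care rate both conditions then have probability r under no effect.
- Include the period term in the log-link model in 11.3. It is still needed because the usual-care rate may itself change after the lecture and through contamination.

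The cost is a few sentences and slightly more analysis work. The readings are already planned, so no new data collection is needed. The change should be made before outcome data are examined and not left to the later SAP.
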